# 7. TRIAL TREATMENT / INTERVENTION

# 7.1. Patient pathway

Randomisation into the trial will be considered the first visit (Visit 1) in the trial. Subsequent visits will depend on whether the participant has become pregnant. At this first visit, baseline medical details will be collected by staff prior to ovulation induction (OI) lasting up to six months. Participants will also be given a treatment diary to complete during the trial.

Should pregnancy be confirmed, participants will be advised to contact the trial team and arrange for Visit 2. At six months, if the participant has not contacted the research team, a member of the site team will call the participant to determine whether they have become pregnant. If a pregnancy is confirmed, Visit 2 may be booked at this point. Visit 2 is only for participants who have become pregnant. They will be asked to return any unused OI drugs and collect additional Metformin/placebo supply to last until 14 weeks gestation.

For participants who have not become pregnant by the end of the six months, the compliance assessment and end of study forms should be completed. Participants may return unused drugs at their next routine fertility clinic appointment.

Please see Figure 7 for an illustration of the participant pathway.

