#### 9.4.2 Events that require expedited reporting to the Sponsor on the SAE Form

All SAEs (except those listed in Sections 9.4.1) from the date of commencement of protocol defined treatment until the end of participant follow-up.

Therefore, for all SAEs the Investigator will do one of the following three procedures:

- 1. record protocol-exempt SAEs in the medical notes but such events do not require reporting to the sponsor
- 2. where the SAE does not require expedited (immediate) reporting it should be reported to the trials office as soon as reasonably possible after becoming aware of the event. This includes expected SAEs as defined in section 9.4.2 above
- 3. where the event requires expedited reporting (immediately and within 24hrs on the Investigator becoming aware of the event) to the trials office.

**Note:** when an SAE occurs at the same hospital at which the participant is receiving trial treatment or is being followed up for trial purposes, processes must be in place to make the trial team at the hospital aware of any SAEs, regardless which department first becomes aware of the event, in an expedited manner.

**LOCI PROTOCOL** Sponsor's reference: RG\_18-272 v1.0 07-Nov-2019 Page 39 of 57 IRAS ID: 257918 EudraCT number: 2018-004641-16 ISRCTN: TBC

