- Serious adverse events

Side effects attributed to clomifene/letrozole and metformin/placebo (nausea or vomiting/abdominal pain/headache/joint pain/fatigue/mood changes/breast discomfort/visual symptoms/hot flushes) will also be tabulated during the ovulation induction and pregnancy phases.

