4.6. Randomisation

Participants will be randomised online via a secure internet facility at the level of the individual in a 1:1 ratio to either letrozole or clomifene and at the same time randomised to metformin or placebo.

A minimisation algorithm will be used within the online randomisation system to ensure balance in the treatment allocations (both randomisations will occur simultaneously, effectively resulting in four allocation groups) over the following variables:

- maternal age (<35 and ≥35 years);
- body mass index (<30 and \geq 30 kg/m²);
- any previous pregnancy (yes and no);
- previous exposure to either clomifene or letrozole;
- any menstrual periods in the preceding 6 months (yes and no);
- randomising centre

A 'random element' will be included in the minimisation algorithm, so that each participant has

a probability (unspecified here) of being randomised to the opposite treatment that they would have otherwise received.

Full details of the randomisation specification will be stored in a confidential document at BCTU.

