4.8. Framework

The objective of the trial is to test the superiority of one intervention to another in the three trial comparisons (see section 4.12 for list of these comparisons).

The null hypothesis is that there is no difference in the proportion of women randomised who experience a live birth at and beyond 34 weeks of gestation between the intervention groups. The alternative hypothesis is that there is a difference between the groups.

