5.1. Confidence intervals and p-values

For all primary and secondary outcomes, estimates of differences between groups will be presented with measures of uncertainty (95% confidence intervals), unless otherwise stated. For the primary outcome, a p-value will be produced, with statistical significance considered at the 5% level. A 95% confidence interval will be utilised. P-values will be presented for the safety outcomes (see section 5.2).

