 - Maternal adverse events (tabulated but not formally analysed), multiple pregnancies, ovarian hyperstimulation syndrome (OHSS), serious adverse events (SAEs): all randomised participants
 - Side effects attributed to clomifene/letrozole and metformin/placebo: all randomised participants

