9.8. Safety data

The number and percentage of participants experiencing any serious adverse events (SAEs) and suspected unexpected serious adverse reactions (SUSARs) will be presented by intervention group. Statistical significance will be determined (p-value generated) through examination of the associated chi-squared statistic. The total number of SAEs and SUSARs in each group will also be given along with a descriptive table of the details of the events. For side effect data, summary statistics (e.g. frequency and percentage) will be detailed only.

A template for reporting this safety data will be given in a separate template report.

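### SAEs and pregnancy-phase side effects are compared over all randomised women although safety follow-up is longer for women who conceive, so a fertility benefit can show up as a modest safety excess.

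*SAP*

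**What the plan says.** **Collection.** Protocol 9.4.2 has SAEs reported "from the date of commencement of protocol defined treatment until the end of participant follow-up", apart from the exemptions in 9.4.1. Protocol 7.1 closes the study for women without a pregnancy: "For participants who have not become pregnant by the end of the six months, the compliance assessment and end of study forms" are to be completed. For women who conceive, the schedule of assessments (Protocol 8.2, SAP Appendix C) runs to Day 28 neonatal and maternal outcomes. Protocol 9.3 records adverse events over the treatment period, which extends to 14 weeks of pregnancy. SAP 9.5 counts conceptions up to 240 days, which is longer than six months.

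**Analysis.** SAP 5.3 gives SAEs the denominator of all randomised participants, and SAP 9.8 attaches a p-value: "Statistical significance will be determined (p-value generated) through examination of the associated chi-squared statistic". SAP 5.2 leaves safety tests unadjusted for multiplicity. Side effects "will also be tabulated during the ovulation induction and pregnancy phases" (SAP 4.4), with the population set in SAP 5.3 as "Side effects attributed to clomifene/letrozole and metformin/placebo: all randomised participants". They are descriptive only. SAP 9.10 limits sensitivity analyses to the primary outcome.

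**The concern.** The time during which a woman can contribute a safety event depends on whether she conceives, and conception is what the treatments are meant to change. If one arm has more pregnancies, more of its women are observed through pregnancy, delivery and the neonatal period. Even with identical toxicity, that arm is expected to show more women with an SAE and more with pregnancy-phase side effects, because only women who conceive have a pregnancy phase. Nausea or vomiting, fatigue and breast discomfort, all on the SAP 4.4 list, are also symptoms of pregnancy itself.

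The SAE contrast carries a p-value, and no analysis in the SAP would separate an excess due to fertility from one due to the drug. At stake is how the safety result is read, since part of a benefit could be reported as harm.

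**Working it through.** **Inputs from the documents.** Live birth at or beyond 34 weeks is 39% vs 29% for comparisons A and B, with 1600 randomised, hence 800 per arm (SAP 4.7; allocation "in a 1:1 ratio to either letrozole or clomifene", SAP 4.6). SAP 5.1 sets the primary outcome test "with statistical significance considered at the 5% level". I carry that level over to the SAE test. I take it as two-sided from SAP 4.8: "The alternative hypothesis is that there is a difference between the groups".

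**Assumptions.** The documents give no SAE rates. Let s be the SAE risk in the induction phase and q the risk from conception onward, equal in both arms. The live-birth rate π stands in for the share entering pregnancy follow-up. It is a low-end figure, because more women conceive than deliver.

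**Formula for the chance of p<0.05.** With n per arm, d = p₁ − p₂ and p̄ = (p₁ + p₂)/2:
- se₀ = √[2p̄(1 − p̄)/n]
- se₁ = √[(p₁(1 − p₁) + p₂(1 − p₂))/n]
- chance = Φ[(d − 1.96·se₀)/se₁] + Φ[(−d − 1.96·se₀)/se₁]

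**The plan's own figure.** n = 760, 39% vs 29%: se₀ = 0.0243, se₁ = 0.0242, and (0.10 − 0.0476)/0.0242 = 2.17, giving 98.5%. SAP 4.7 states 98.5%.

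**Observation time.** Assume 13 months for conceivers and 6 for the others.
- 0.39 × 13 + 0.61 × 6 = 8.73 months
- 0.29 × 13 + 0.71 × 6 = 8.03 months
- Ratio 1.09. If non-conceivers are followed for 8 months: 9.95 vs 9.45, ratio 1.05.

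**Pregnancy-phase side effects over all randomised women.** With the same risk t per pregnancy, the ratio is 0.39t/0.29t = 1.34 (0.44/0.34 = 1.29 for comparison C). At t = 30% (assumed) this is 11.7% vs 8.7%. Per pregnant woman the ratio is 1.00.

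**Any SAE.** P(any SAE) = 1 − (1 − s)(1 − πq), n = 800, no drug effect:

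| s | q | Any SAE | RR | Chance of p<0.05 |
|---|---|---|---|---|
| 1% | 2% | 1.8% vs 1.6% | 1.13 | 6.1% |
| 1% | 5% | 2.9% vs 2.4% | 1.20 | 9.4% |
| 0 | 2% | 0.78% vs 0.58% | 1.34 | 7.8% |
| 0 | 5% | 1.95% vs 1.45% | 1.34 | 12.1% |
| 1% | 10% | 4.9% vs 3.9% | 1.26 | 16% |
| 1% | 20% | 8.7% vs 6.7% | 1.29 | 32% |

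Example, row 4: d = 0.005, se₀ = 0.00646, se₁ = 0.00646, giving Φ(−1.19) + Φ(−2.73) = 0.118 + 0.003 = 0.121.

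At s = 1% the excess is 800 × 0.00198 = 1.6 women for q = 2% and 800 × 0.00495 = 4.0 women for q = 5%. Row 3 expects only 6.2 vs 4.6 women, so the normal approximation is rough there; summing exactly over the two binomial distributions gives 6.7%.

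**Comparison C** (400 per arm, 44% vs 34%, s = 1%): 5.5% at q = 2%, 10% at q = 10%.

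**Smaller benefit** (36.5% vs 31.5%, 800 per arm, s = 1%): 5.3% at q = 2%, 6.1% at q = 5%.

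**The case against.** The strongest counter-argument is Protocol 9.4.1. It keeps off the SAE form admissions for hyperemesis, early bleeding, pregnancy loss, complications of pregnancy, birth and post-natal care, and neonatal admissions for sepsis or prematurity. SAP 9.4 takes SAEs from that form. Most of what happens in the extra follow-up therefore never enters the test, and the last two rows of the table are hard to defend. This stands. It does not remove the effect, because 9.4.1 also exempts admissions unrelated to ovulation induction or pregnancy. The events that remain, such as congenital anomalies, deaths and life-threatening events, may lean towards pregnancy. The ratio can then stay near 1.34, but on few events.

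The all-randomised comparison is also a valid intention-to-treat estimate of total SAE burden. A reader might infer that it should be replaced by a test closing at six months. The documents do not support that. Metformin or placebo continues to 14 weeks of pregnancy, so such a window would drop on-treatment time in later conceivers and nearly all pregnancy and neonatal SAEs from the randomised test.

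The plan already covers part of the ground. Side effects are split by phase and untested, congenital abnormalities use babies born alive as denominator, and SAP 9.8 adds a descriptive table of events. The separate template report is not available here and may show further denominators, but the population written in SAP 5.3 is all randomised.

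Finally, six months is the time of a form. Conception counts to 240 days, and the end of SAE follow-up for non-conceivers is not given in days.

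**Conclusion.** The point holds in a limited form. Follow-up depends on conception, and the planned SAE test and pregnancy-phase side-effect tables make no allowance for that. For side effects the mismatch of denominator and phase is plain: a ratio of about 1.34 at the planning rates with no drug effect, though no p-value is attached. For SAEs the expected excess is probably small. The chance of p<0.05 without toxicity is about 6 to 12% against a nominal 5%, given an assumed residual pregnancy-phase risk of 2 to 5%, an induction-phase risk of 0 to 1%, and a true 39% vs 29% difference.

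A reader might infer that the more effective arm must look less safe by construction, or that false signals of 16% or 32% are likely. The documents do not support either. The excess appears only if SAEs accrue in the extra follow-up, the larger figures need pregnancy-phase risks of 10 to 20% after the exemptions, and the 10-point difference is the one the trial was sized to detect. If the true difference is 5 points, the SAE effect nearly vanishes.

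**What to change.** In SAP 5.3 and 9.8, with a matching clarification in the protocol:

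1. Keep the all-randomised SAE comparison and label it as total burden, pregnancy included.
2. Define the end of SAE follow-up for women who do not conceive, and reconcile six months (Protocol 7.1) with 240 days (SAP 9.5).
3. Beside the main result, report SAEs by phase: induction over all randomised women, pregnancy over women who conceived, neonatal over babies. Add a common-window or exposure-adjusted comparison as supportive. Observation time should be shown with the induction table, because women leave that phase on conceiving.
4. Tabulate pregnancy-phase side effects also over women who entered that phase, labelled as a non-randomised subset. SAP 5.3 already gives pregnancy-end outcomes a supportive denominator of this kind.

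The cost is some wording and a few extra tables. The phase split needs event dates, and the documents do not show the SAE form's contents, so this should be checked. The per-pregnancy tables are not protected by randomisation and should support, not replace, the all-randomised result.

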9.9. Planned subgroup analyses

Subgroup analyses will be restricted to the primary outcome only. BMI (<30 and \geq 30 kg/m²) is the single key subgroup of interest (i.e. we propose to be able to draw firm conclusion about any differential effect with respect to this variable only). The following subgroup analyses will be considered exploratory:

From the minimisation algorithm -

- Maternal age (<35 and ≥35 years);
- Body mass index (<30 and \geq 30 kg/m²);
- Any previous pregnancy (yes and no);
- Previous exposure to either clomifene or letrozole;
- Any menstrual periods in the preceding 6 months (yes and no);

As well as the following variables –

- Ethnicity (White/South Asian/Black/Other)
- History of previous miscarriage $(0/1-2/\geq 3)$
- Androgen excess confirmed clinically or through laboratory testing (yes and no) see section 9.4 Data manipulations on derivation details
- Insulin resistance confirmed clinically or laboratory testing (yes and no) see section 9.4 Data manipulations on derivation details.

Tests for interaction will be performed by including the treatment group by subgroup interaction parameter in the statistical model. A p-value for this parameter will be produced. Given there is only one key subgroup of interest, no adjustments will be made for multiple testing on this p-value.

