Following review by the funder (NIHR HTA) and due to the impact of the COVID-19 pandemic on participant accrual, the sample size target was revised on 3 February 2023 to aim for at least 80% power within the letrozole plus metformin vs clomifene plus metformin comparison, rather than the 90% power originally described. 800 participants (with primary outcome data gained on 760) within this comparison would provide 81% power (p=0.05) to detect a difference of 10% between groups (the same assumptions of 44% and 34% in the two groups as previously stated).

Due to the factorial design, this agreement would mean a sample of 1600 participants (with primary outcome data gained on 1520 assuming 5% loss to follow-up) within the two main comparisons (letrozole vs clomifene and metformin vs placebo). This number of participants would provide 98.5% power (at p=0.05) to detect a difference of 10% between groups (the same assumption of 39% vs 29% in both comparisons as previously stated).

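### The plan promises a firm conclusion on effect modification by BMI, but the trial is sized for main effects only and the interaction test has low power

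*SAP*

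**What the plan says.** SAP 9.9 limits subgroup analyses to the primary outcome and singles out BMI, split at 30 kg/m², as the one key subgroup. Its stated purpose is that "we propose to be able to draw firm conclusion about any differential effect with respect to this variable only". Protocol 13.2.3 has the same sentence.

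The method is a standard interaction test: "Tests for interaction will be performed by including the treatment group by subgroup interaction parameter in the statistical model". On multiplicity, the SAP says "Given there is only one key subgroup of interest, no adjustments will be made for multiple testing on this p-value".

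The SAP then introduces a list with "The following subgroup analyses will be considered exploratory", and BMI appears in that list as well. In protocol 13.2.3 it is the other subgroups that are exploratory.

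SAP 4.7 gives power for main effects only. After the revision of February 2023 it is 98.5% for the two marginal comparisons (A, letrozole versus clomifene; B, metformin versus placebo) and 81% for comparison C (letrozole plus metformin versus clomifene plus metformin). SAP 9.10, on the drug-by-drug interaction, adds in general terms that interaction tests will lack power.

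**The concern.** A firm conclusion about any differential effect includes the conclusion that there is none. To support that, the trial would need good power for a BMI interaction of a size that matters, or a confidence interval narrow enough to exclude one. A sample chosen for main effects does not normally provide either. With an even split, the standard error of a difference between two subgroup effects is twice that of the overall effect. The sentence also passed unchanged from protocol to SAP while the recruitment target fell from 2,100 to 1,600.

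BMI is the only subgroup for which the plan promises a conclusion, so it is the one that readers would rely on. If the test is not significant, that sentence invites them to take it as settled that BMI makes no difference, when a large interaction could easily have been missed.

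**Working it through.** **Inputs from the documents**
- A and B: 1,600 randomised, "with primary outcome data gained on 1520 assuming 5% loss to follow-up", so 760 per arm; rates 39% versus 29% (SAP 4.7).
- C: 800 randomised, 760 analysed, so 380 per arm; rates 44% versus 34% (SAP 4.7).
- Significance for the primary outcome: "with statistical significance considered at the 5% level" (SAP 5.1). Two-sided testing is inferred from SAP 4.8: "The alternative hypothesis is that there is a difference between the groups".
- The primary p-value comes from the log-link model (SAP 9.5).

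**Assumptions, because the documents are silent**
- BMI split: 50:50 as base case, 30:70 as an alternative.
- Interaction size: 10 points, taken from the minimally important main effect. An example is an effect of 5 points in one BMI stratum and 15 in the other.

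**Step 1. Reproduce the plan's own power.** With p̄ the mean rate and n the number per arm,

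power = Φ{(0.10 − 1.96·√[2p̄(1−p̄)/n]) / √[(p₁(1−p₁)+p₀(1−p₀))/n]}

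- A/B: (0.10 − 1.96 × 0.02430)/0.02417 = 2.17, giving 98.5%.
- C: (0.10 − 1.96 × 0.03539)/0.03520 = 0.87, giving 80.8%.

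Both match the SAP, so the inputs are read correctly.

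**Step 2. Interaction on the risk-difference scale.** With N analysed, a fraction f in one BMI stratum and v = p̄(1−p̄),

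SE = √[4v/(Nf) + 4v/(N(1−f))], power = Φ(0.10/SE − 1.96)

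Here v = 0.34 × 0.66 = 0.2244 for A/B and 0.39 × 0.61 = 0.2379 for C. The difference detectable with 80% power is (1.96 + 0.84) × SE.

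| | Split | SE (points) | Power, 10 points | Detectable with 80% power |
|---|---|---|---|---|
| A/B | 50:50 | 4.86 | Φ(2.06 − 1.96) = 54% | 13.6 points |
| A/B | 30:70 | 5.30 | Φ(1.89 − 1.96) = 47% | 14.9 points |
| C | 50:50 | 7.08 | Φ(1.41 − 1.96) = 29% | 19.8 points |
| C | 30:70 | 7.72 | Φ(1.30 − 1.96) = 25% | 21.6 points |

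Using the separate variance of each cell instead of a common one changes the 50:50 figures by less than one point. Simulation at 50:50 gave 54.8% and 29.8%. The 95% confidence interval at 50:50 has a half-width of 1.96 × SE, or 9.5 points (A/B) and 13.9 points (C).

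**Step 3. The same 10-point interaction on the scale of the planned p-value.** At a 50:50 split each arm-by-BMI cell holds N/4 women. The interaction is the difference of the two log risk ratios, and

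SE = √[Σ((1−p)/p)/(N/4)], summed over the four cells.

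*Equal control rates in both strata*
- A/B, 44% versus 29% and 34% versus 29%: 0.258/0.146 = 1.76, power 42%.
- C, 49% versus 34% and 39% versus 34%: 0.228/0.185 = 1.24, power 23%.

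*Control rates 10 points apart (assumption)*
- Larger effect in the low-rate stratum. A/B (39% v 24%; 39% v 34%): 0.348/0.147 = 2.37, power 66%. C (44% v 29%; 44% v 39%): 0.296/0.186 = 1.59, power 36%.
- Larger effect in the high-rate stratum. A/B (29% v 24%; 49% v 34%): 0.176/0.150 = 1.17, power 22%. C (34% v 29%; 54% v 39%): 0.166/0.189 = 0.88, power 14%.

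None of these scenarios reaches 80%.

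**The case against.** **The sentence may only rank BMI above the other subgroups.** It sits in a parenthesis, and the SAP says only that a p-value will be produced. A reader might infer that the plan commits to reading a non-significant test as proof of no BMI difference. It does not say so, and this point should not be put that strongly. What stands is that the sentence covers any differential effect, and pre-specification guards against selective reporting without adding precision.

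**The 54% and 29% are not properties of the planned test.** This is right. They depend on the risk-difference scale, an even split and a borrowed interaction size. Nor are they upper bounds, since log-scale power for A/B can reach 66%. They should not be written into the SAP as bare figures.

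**The plan already admits the weakness.** SAP 9.10 does so in general wording, but in a bullet about the drug-by-drug interaction, and SAP 9.9 claims the opposite for BMI. The two need reconciling.

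**Multiplicity.** A reader might infer that testing BMI in several comparisons contradicts the reason given for not adjusting. The documents do not support that. SAP 4.12 and 5.2 declare the comparisons distinct questions with no adjustment across them, and the sentence in 9.9 concerns the number of subgroup variables. SAP 4.12 also labels the two further comparisons exploratory.

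**The repeated BMI entry.** The exploratory list copies the minimisation variables apart from centre, and the preceding sentence and the protocol make the intended status clear. This is a drafting slip.

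**Conclusion.** The point holds as a correction to a stated claim. The documents give no basis for a firm conclusion on BMI, and their own inputs show that the design cannot provide one. For an interaction as large as the minimally important main effect, power at an even split is about 54% (A/B) and 29% (C) on the risk-difference scale. On the log scale it is about 42% and 23% with equal control rates, ranging over 22–66% and 14–36% when control rates differ by 10 points. On the risk-difference scale a more uneven split lowers power, and a smaller interaction would have less still.

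A non-significant result therefore cannot support a firm statement that BMI does not modify the effect. At an even split, an estimate of zero would leave interactions of up to about 9.5 points (A/B) or 13.9 points (C) inside the confidence interval.

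The exact figures rest on the assumed split, interaction size and control rates. The conclusion does not depend on any one of them, since no scenario tried reaches 80%. The primary analysis and the choice of BMI as key subgroup are unaffected.

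**What to change.** In SAP 9.9 and protocol 13.2.3, replace the firm-conclusion wording with text such as:

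> *BMI (<30 and ≥30 kg/m²) is the one key pre-specified subgroup. For each comparison the treatment-by-BMI interaction will be reported as an estimate with its 95% confidence interval and interpreted as supportive. A non-significant interaction test will not be taken as evidence that the effect is the same in both BMI groups.*

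If a power or detectable-difference figure is added, state its scale, the assumed BMI split and the interaction size.

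Also:
- bring 9.9 into line with the statement on interaction power in SAP 9.10;
- remove BMI from the exploratory list in SAP 9.9.

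The cost is wording in both the SAP and the protocol, and a less favourable stated claim. Design, data collection and the analysis model do not change.
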